3.2 Study and Treatment Duration

The total duration of the study will be approximately 4 years although patients will be treated until meeting a discontinuation criterion. The duration of study participation for each patient includes the following:

- **Screening Period:** Up to 30 days
- **Treatment Period:** 28 days per cycle or until death, intolerable adverse events, progressive disease or other protocol-specified reasons for patient withdrawal
- **End-of-Treatment Visit:** 30 (±5) days after the last dose of poziotinib
- **Long-Term Follow-up:** After treatment period discontinuation in Study SPI-POZ-203, patients who have consented will be contacted every 3 months, for up to 2 years after patient’s first dose of poziotinib, for survival assessment

The study design diagram is presented in **Figure 17** and the Schedule of Study Assessments and Procedures is presented **Appendix 1**.

Figure 17 Diagram of Study Design

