
Duration of Study: The total duration of the study will be approximately four (4) years, including enrollment and follow-up. The duration of study participation for each patient includes the following:
 
 Screening Period: Up to 30 days Treatment Period: 28 days per cycle for up to 24 months of treatment or until death, intolerable adverse events, progressive disease or other protocol-specified reasons for patient withdrawal End-of-Treatment Visit: 30 (±5) days after the last dose of poziotinib Long-Term Follow-up: After treatment period discontinuation, patients who have consented will be contacted every 3 months, for up to 2 years after patient’s first dose of poziotinib, for survival assessment. 	

Patient Replacement Strategy: Patients not efficacy evaluable i.e. not completed at least 1 cycle of poziotinib treatment and have baseline and at least 1 post-baseline tumor response evaluation using RECIST, version 1.1 (and/or RANO for Cohort 4) will be replaced unless they have discontinued from treatment or from the study due to disease progression or probable disease progression (eg. clinical progression, initiation of new therapy) or due to toxicity.
	

Study Design and Methodology
 
This is a Phase 2 multicenter, open-label study to evaluate the efficacy and safety of poziotinib in patients with EGFR or HER2 mutation-positive malignant solid tumors.
	

The study is a basket trial with five cohorts. The primary analysis will be conducted for each cohort separately. The five cohorts are:

- **Cohort 1:** Patients that have HER2-positive or HER2-negative, breast cancer with HER2 activating mutations (see **Table A**) (N=30) (See **Inclusion Criteria #4**)
- **Cohort 2:** Patients that have colorectal cancer with HER2 activating mutations (see **Table A**) (N=30)
- **Cohort 3:** Patients that have solid tumors (except NSCLC, breast cancer, or colorectal cancer) with HER2 activating mutations (see **Table A**) (N=30)
- **Cohort 4:** Patients that have GBM with EGFR activating mutations (see **Table A**) (N=30)
- **Cohort 5:** Patients that have solid tumors (except NSCLC or GBM) with EGFR activating mutations (see **Table A**) (N=30)

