4.3 Patient Discontinuation/Withdrawal Criteria

Patients can withdraw from participation in this study at any time, for any reason, specified or unspecified, and without prejudice.

All treated patients must be withdrawn from the study due to the following reasons:

- Development of an adverse event (AE) that interferes with the patient's participation
- Initiation of non-protocol therapy
- Development of progressive disease (PD)
- Patient withdrawal of informed consent
- Delay of poziotinib administration for >28 days since last study drug administration
- Investigator decision
- Sponsor decision

- Lost to follow-up
- Pregnancy
- Death

The reason for the patient discontinuing study treatment or terminating from the study must be recorded on the case report form (CRF). Patients who discontinue treatment or who are withdrawn from treatment will return for an End-of-Treatment Visit 30 (± 5) days after the last dose of poziotinib or prior to beginning a new treatment, whichever is first. If death is recorded as the reason for study discontinuation, the cause of death should be recorded on the CRF. Patients not efficacy evaluable i.e. not completed at least 1 cycle of poziotinib treatment and have baseline and at least 1 post-baseline tumor response evaluation using RECIST, version 1.1 (and/or RANO for **Cohort 4**) will be replaced unless they have discontinued from treatment or from the study due to disease progression or probable disease progression (eg. clinical progression, initiation of new therapy) or due to toxicity.

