5.3.9 Long-Term Follow-up – Every 3 Months

- After progressive disease is documented, regardless of possible treatment continuation, patients who have consented will be contacted by phone or email (or letter if specifically requested) every 3 months, for up to 2 years after patient's first dose of poziotinib, for survival assessment
- Record SAEs where a causal relationship with the study drug is suspected.

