8.4 General Statistical Methods

The Sponsor's Biostatistics and Data Management group will be responsible for data management and statistical analysis of this study. All statistical analyses will be performed using SAS for Windows (Version 9.4 or higher). Patient data listings and tabular presentations of results will be provided. Further details of the criteria and conduct of the statistical analyses will be included in the SAP for this study.

8.5 Efficacy Analysis:

The primary efficacy variable ORR is the proportion of patients with confirmed Complete Response (CR) and Partial Response (PR) recorded from the start of the first dose of poziotinib to the end of study and will be analyzed descriptively along with the 95% CI for each cohort. The determination of ORR will be based upon an assessment of the local radiological review by the respective Principal Investigator using RECIST version 1.1 and/or RANO criteria (for GBM). Confirmatory assessments must be completed by the Investigator 4 weeks \pm 3 days after the first assessment of CR or PR and only confirmed CR/PR can be deemed as CR/PR.

The secondary endpoints are DCR and DoR, DCR is the proportion of patients with best response of CR, PR, and Stable Disease (SD) from the first dose of poziotinib to the end of study; and DoR is the time from the date that measurement criteria are first met for CR or PR (whichever status is recorded first) until the first subsequent date that progressive disease or death is documented.

Exploratory endpoints are OS and PFS. OS is the time from the treatment start date to the date of death during the study and PFS is the time from the treatment start date to the date of documented disease progression or death during the study.

DCR, DoR, OS, and PFS will be analyzed using descriptive statistics, for each cohort, and with 95% CI for DCR and Kaplan-Meier plot for DoR, OS, and PFS.

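### If treatment can run past month 24, the exploratory OS curve is biased upward after that point; the documents disagree on whether it can, and no OS horizon is set

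*Combined protocol and SAP*

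**What the plan says.** **Survival contact.** Under Section 3.2, once treatment has ended, "patients who have consented will be contacted every 3 months, for up to 2 years after" the first dose. Section 5.3.9 starts contact at documented progression and has the same limit: "patients who have consented will be contacted by phone or email (or letter if specifically requested) every 3 months, for up to 2 years after" first dose.

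**Treatment length.** The Synopsis, under Duration of Study, gives "28 days per cycle for up to 24 months of treatment or until death, intolerable adverse events, progressive disease". Section 3.2 gives "28 days per cycle or until death, intolerable adverse events, progressive disease or other protocol-specified reasons for patient withdrawal", and adds: "The total duration of the study will be approximately 4 years although patients will be treated until meeting a discontinuation criterion". The design text of the Synopsis and Section 3.1 also end treatment only on events such as progression, intolerable toxicity, new therapy or death.

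**Leaving the study.** Section 4.3 makes progression a mandatory reason for withdrawal. The last visit is "30 (±5) days after the last dose of poziotinib". Treatment after progression moves to the extension study SPI-POZ-501, and nothing says that its survival data enter this analysis.

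**Analysis.** Section 8.5 states: "OS is the time from the treatment start date to the date of death during the study". OS is exploratory, described per cohort with a Kaplan-Meier plot. No censoring rule or time horizon is given. Section 8 promises a SAP before database lock, and Section 8.4 leaves further detail to it.

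**The concern.** Kaplan-Meier needs patients censored at a given time to have the same later death risk as those who remain. On the text without a treatment limit, this fails at month 24. Patients who have progressed and are alive leave the risk set because contact ends. Patients still on drug stay, and under Section 4.3 they are progression-free.

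When one of them later progresses, the 2-year contact period has already passed, so only deaths up to about the End-of-Treatment visit can be counted. The curve after month 24 therefore applies the low death rate of long-term progression-free patients to all survivors.

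At stake is a late plateau created by the follow-up rule. Where more than half of a cohort is alive at month 24, the reported median would also be too long.

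**Working it through.** **The plan's own figures.** The documents state no OS rate, event count or horizon, so there is no OS figure to reproduce. The two-stage design for ORR (0 of 9, then 3 of 30; 5% versus 25%) does reproduce: early termination 0.630, expected size 16.76, error rates 0.049 and 0.098. It is not affected by this point.

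**Inputs from the documents.** 30 patients per cohort; survival contact to month 24; End-of-Treatment visit at about 1 month; no treatment limit (Section 3.2 reading).

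**Assumptions, not in the documents.** Constant hazards; median time to progression 6 or 12 months; death before progression m0 = 0.005 or 0.01 per month; death after progression m1 = 0.04 or 0.06 per month. All patients consent to follow-up and have at least 36 months of potential follow-up.

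**Formulas.** With λ = ln 2 / median and a = λ + m0:

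- Progression-free and alive: PF(t) = exp(−a·t)
- Progressed and alive: PA(t) = λ[exp(−m1·t) − exp(−a·t)] / (a − m1)
- True OS: S(t) = PF(t) + PA(t)
- After month 24 the risk set is PF(t) plus those who progressed within the past month, w·PF(t), where w = λ[exp(a − m1) − 1] / (a − m1)
- Death rate in that risk set: h = (m0 + w·m1) / (1 + w)
- Kaplan-Meier limit: KM(t) = S(24)·exp[−h(t − 24)]

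**One case in full** (median 6, m0 0.005, m1 0.06). λ = 0.1155 and a = 0.1205. PF(24) = 0.0554 and PA(24) = 0.3464, so S(24) = 0.402. w = 0.119 and h = (0.005 + 0.119 × 0.06)/1.119 = 0.0109. KM(36) = 0.402 × exp(−0.130) = 0.353. True S(36) = 0.208. Excess: 14.5 points.

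**All eight cases** (OS in %; excess in points, from unrounded values; at-risk counts are expected numbers out of 30):

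| Median, m0, m1 | S(24) | Month 30 true / KM (excess) | Month 36 true / KM (excess) | At risk after 24 / at 36 |
|---|---|---|---|---|
| 6, 0.005, 0.04 | 52.5 | 42.0 / 49.8 (7.8) | 33.4 / 47.3 (13.9) | 1.9 / 0.4 |
| 6, 0.005, 0.06 | 40.2 | 29.1 / 37.7 (8.5) | 20.8 / 35.3 (14.5) | 1.9 / 0.4 |
| 6, 0.01, 0.04 | 50.0 | 39.9 / 46.2 (6.3) | 31.6 / 42.7 (11.0) | 1.7 / 0.4 |
| 6, 0.01, 0.06 | 38.0 | 27.4 / 34.7 (7.3) | 19.5 / 31.6 (12.1) | 1.7 / 0.4 |
| 12, 0.005, 0.04 | 63.1 | 53.0 / 60.5 (7.5) | 44.1 / 58.0 (14.0) | 7.0 / 3.3 |
| 12, 0.005, 0.06 | 54.0 | 42.7 / 51.4 (8.7) | 33.3 / 49.0 (15.7) | 7.0 / 3.3 |
| 12, 0.01, 0.04 | 58.4 | 48.5 / 54.5 (6.0) | 39.9 / 50.8 (10.9) | 6.2 / 2.8 |
| 12, 0.01, 0.06 | 49.6 | 38.6 / 46.0 (7.3) | 29.6 / 42.6 (13.0) | 6.2 / 2.8 |

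The number at risk is 30·PF(t)·(1 + w).

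**Second set of assumptions.** A simulation of 400,000 patients used median PFS 4 to 12 months, median survival after progression 8 to 18 months, and 10% of PFS events being deaths. Kaplan-Meier exceeded true OS by 5 to 8 points at month 30 and 7 to 15 at month 36 (from 15.3% against 7.8% up to 50.9% against 35.8%). At month 23.9 the two agreed in every scenario.

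**Effect on the median.** In the sixth row the true median is 26.0 months. The plan's curve reaches 50% only at 24 + ln(0.5395/0.5)/0.00801 = 33.5 months. Where S(24) is below 50%, the median falls before month 24 and is correct.

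**Under the Synopsis limit.** Observation ends at about month 25. The same formula there gives, for the worked case, 0.402 × exp(−0.0109) = 0.397 against a true 0.381. Across the eight cases the excess at month 25 is 1.1 to 1.6 points, and no curve extends further.

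**The case against.** The strongest objection is that the premise is one side of a contradiction. With the Synopsis limit nobody is on drug after month 24, and no tail of consequence remains. That stands: a reader might infer that patients will be observed on drug past 2 years, and the documents do not establish this. They do leave the limit out of three other passages, so it cannot be relied on either.

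A reader might also take a larger bias from the shortcut KM(36) = S(24)·exp(−12·m0), which gives 37.8% against 20.8% and 59.4% against 44.1%, or 15 to 17 points. It ignores deaths in the End-of-Treatment window, which the plan does collect, and uses a single low value for m0. It should not be used.

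The tail is also thin. With 0.44 expected at risk at month 36, the chance that nobody is left is (1 − 0.44/30)^30 = 0.64, so that estimate would often not exist. The study lasts about 4 years including enrolment, so late entrants may not reach month 36. A cohort stopped at stage 1 has 9 patients.

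Finally, OS is exploratory and descriptive, and the SAP, which is not among the documents, could still set a horizon. Both points stand and lower the weight. They do not remove the problem, because the present text, followed without a treatment limit, produces the biased curve.

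**Conclusion.** The point holds conditionally. The passages on treatment length conflict and must be reconciled; which is right is not judged here. If treatment can pass month 24, censoring there depends on progression status and the OS curve is biased upward from that point: about 6 to 9 points at month 30 and 11 to 16 at month 36 under the tabulated hazards, or 5 to 8 and 7 to 15 under the second set. All hazards are assumptions.

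A reader might infer that the trial's OS results in general are unreliable. The documents do not support that. Rates up to month 24 and any median below 24 months are unaffected, as are ORR, DCR, DoR and the two-stage rule. This is a cheap improvement of minor weight.

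**What to change.** Reconcile the Synopsis duration paragraph with the Synopsis design text and Sections 3.1 and 3.2 on treatment length.

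In Section 8.5, the Synopsis and the SAP, add: All patients alive at 24 months after first dose, on or off treatment, are censored at 24 months; the OS curve, median and landmark rates are not reported beyond 24 months.

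This is valid under either reading of treatment length. It costs one sentence, with no extra contacts or patients. The downside is that the curve stops at 24 months and the median is not estimable if more than half are alive then; the rule prevents a wrong late median but does not recover the right one. If later survival is wanted, the alternative is equal survival contact for all patients beyond month 24, on or off drug, which does need extra contacts.

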4 PATIENT POPULATION

The following inclusion and exclusion criteria must be met in order to participate in the study.

4.1 Inclusion Criteria:

1. Males or females 18 years of age or older
2. Patient must be willing and capable of giving written Informed Consent, adhering to dosing and visit schedules
3. Patient has an advanced or metastatic solid tumor with no available standard therapy option
4. Patients with breast cancer must have an NGS HER2 activating mutation (see [Table A](#)), and:
 - IHC HER2-positive tumors (based on ASCO/CAP criteria) are included only when they have progressed on trastuzumab, pertuzumab, and T-DM1 which have been administered in the metastatic setting, unless disease recurred within 12 months of adjuvant or neoadjuvant treatment.
 - IHC HER2-negative, ER/PR-positive breast cancer (based on ASCO/CAP criteria) may be included after 1st line endocrine therapy in the metastatic setting, either as a single agent or in combination with standard biological agents (eg aromatase inhibitor and CDK 4/6 inhibitor). Patients are permitted to continue single agent endocrine therapy concurrently with the study.
 - IHC HER2-negative, ER/PR-negative tumors may be included after first-line treatment (any standard chemotherapy-based regimen) in the metastatic setting.
5. Patient with colorectal cancer who are MSI-H and have confirmed progression on pembrolizumab or nivolumab or nivolumab/ipilimumab
6. Patient's tumor is positive for eligible EGFR or HER2 mutations based on DNA genetic testing of either tumor tissue or plasma samples. Patients with documented EGFR or HER2 mutations are identified by local testing from participating sites using next generation sequencing (NGS) test such as OncoMine Comprehensive Assay (OCA), Guardant360 Assay, or FoundationOne Assay that detects specific mutations, performed by a US CLIA certified and CAP accredited clinical laboratory or similarly accredited lab for ex-US sites using tissue or plasma samples. Patient has a solid tumor with at least one of the listed activating mutations (see [Table A](#)):
 - Cohort 1: Patients that have HER2-positive or HER2-negative breast cancer with HER2 activating mutations (see [Table A](#)) (N=30) (See [Inclusion Criteria #4](#))
 - Cohort 2: Patients that have colorectal cancer with HER2 activating mutations (see [Table A](#)) (N=30)
 - Cohort 3: Patients that have solid tumors (except NSCLC, breast cancer, or colorectal cancer) with HER2 activating mutations (see [Table A](#)) (N=30)
 - Cohort 4: Patients that have GBM with EGFR activating mutations (see [Table A](#)) (N=30)
 - Cohort 5: Patients that have solid tumors (except NSCLC or GBM) with EGFR activating mutations (see [Table A](#)) (N=30)

Table A—List of Activating Mutations Eligible for Enrollment

Activating Mutations	
Cohorts 1-3: HER2 Activating Mutations (at least one of the following)	
Furin-Like/Extracellular	S310F/Y
Transmembrane	I655V, V659E, R678Q, V697L
Kinase Domain	Exon 20 insertion, T733I, L755X, I767M, D769X, V773M, V777X, L786V, V842I, T862I, L869R
Cohorts 4-5: EGFR Activating Mutations (at least one of the following)	
Extracellular & Transmembrane	EGFRvIII, R108K, R222C, A289T, P596L, G598V
Kinase Domain	Exon 20 insertion, E709X, E709_T710del insD, L718X, G719X, I740_K745dupIPVAIK, I740_K745dup, V742I, L747X, E746_A750del, A750P, S768I, S768I/V769L, S768I/V774M, L833V, V769M, V774M, R831C, R831H, L858R, L861Q, A864V

7. Patient has measurable disease, as per the Response Evaluation Criteria in Solid Tumors (RECIST, version 1.1) and/or RANO Criteria for **Cohort 4**. Target lesion(s) must be radiographically measurable. CNS metastatic lesions cannot be considered target lesions in **Cohorts 1-3** and in **Cohort 5**.
8. Brain metastases may be allowed if the patient's condition is stable. Stable condition is defined as having stable neurological symptoms, with no requirement for anti-seizure medications or >2 mg/day dexamethasone equivalent or increasing doses of systemic corticosteroids (except **Cohort 4** where anti-seizure medication [Keppra] and dexamethasone up to or equivalent to 4 mg daily is allowed), and no evidence of CNS disease progression documented for at least 4 weeks after CNS-directed treatment (eg. whole brain radiation), as ascertained by clinical examination and brain imaging (MRI or CT) during the screening period. Patients must complete CNS-directed treatment and return to stable condition prior to eligibility assessment for the study. For patients who have had radiation therapy, post-treatment MRI tests should show no increase in brain lesion size/volume and no new lesions compared to pre-treatment MRI (except **Cohort 4**) for at least 4 weeks. A new lesion is defined as lesion size greater than 5 mm and not previously present.
9. Patient has an Eastern Cooperative Oncology Group (ECOG) performance status 0 or 1.
10. Patient has recovered from prior systemic therapy for advanced or metastatic disease to Grade ≤ 1 for non-hematologic toxicities (except for Grade ≤ 2 peripheral neuropathy or alopecia) and has adequate hematologic, hepatic, and renal function at Baseline, as defined by:
 - Absolute neutrophil count (ANC) $\geq 1.0 \times 10^9/L$
 - Platelet count $\geq 75 \times 10^9/L$
 - Hemoglobin ≥ 9.0 g/dL
 - Total bilirubin $\leq 1.5 \times ULN$; if hepatic metastases are present, $\leq 2.0 \times ULN$

- Aspartate aminotransferase/serum glutamic-oxaloacetic transaminase (AST/SGOT), alanine aminotransferase/serum glutamic-pyruvic transaminase (ALT/SGPT) $\leq 2.5 \times$ upper limit of normal (ULN); if hepatic metastases are present, $\leq 5.0 \times$ ULN
 - Creatinine clearance
 - Creatinine clearance ≥ 50 mL/min (calculated according to Cockcroft and Gault formula: $CCr = \{((140 - \text{age}) \times \text{weight}) / (72 \times \text{SCr})\} \times 0.85$ (if female), Scr in mg/dL)
 - or
 - GFR ≥ 45 ml/min/1.73m² as calculated by the CKD-EPI Creatinine Equation (2009) (https://www.kidney.org/professionals/kdoqi/gfr_calculator)
11. Patient with childbearing potential is willing to practice 2 forms of contraception, one of which must be a barrier method, from study entry until at least 30 days after the last dose of poziotinib.
12. Females of childbearing potential must have a negative serum pregnancy test within 7 days prior to study treatment. Females who are postmenopausal do not require this test (Postmenopausal is defined as any of: age ≥ 60 years, age < 60 years and amenorrheic for 12 or more months in the absence of chemotherapy, tamoxifen, toremifene, or ovarian suppression and follicle-stimulating hormone (FSH) and estradiol in the postmenopausal range, or prior bilateral oophorectomy, or if taking tamoxifen or toremifene, or age < 60 years with FSH and plasma estradiol in postmenopausal ranges).

4.2 Exclusion Criteria:

1. Patient has primary tumors in central nervous system (CNS), meningeal carcinomatosis, leptomeningeal carcinomatosis, spinal cord compression, or unstable brain metastasis except if qualified under inclusion criteria for Cohort 4.
2. Patients with the T790M mutation in EGFR.
3. Patients with breast or gastric cancers without eligible HER2 mutations (see [Table A](#)).
4. Patient has received anticancer chemotherapy, biologics, immunotherapy, targeted therapy (including HER2 targeted therapy), curative-intent radiotherapy, or other investigational treatment within 15 days of study entry. Palliative local radiation therapy for bone metastasis may be allowed. Standard and approved hormonal therapies for hormonal receptor positive tumors are allowed. For Cohort 4, patients who have received prior single agent VEGF inhibitor therapy (eg bevacizumab) are excluded.
5. Patient has used or will continue to use strong inhibitors/inducers of CYP3A4 and CYP2D6 within 2 weeks prior to or during the study.
6. Patient has not recovered (i.e., $>$ Grade 1) from drug-induced pancreatitis or has a history of drug-induced pancreatitis.
7. Patient has interstitial lung disease (ILD) or history of ILD or pneumonitis or is less than 30 days from last dose of CPI.
8. Patient has \geq Grade 2 skin disorders (rash), mucositis, or stomatitis within previous 15 days.

9. Patient has a history of congestive heart failure (CHF) Class III/IV according to the New York Heart Association (NYHA) Functional Classification or serious cardiac arrhythmias requiring treatment.
10. Patient has a high risk of cardiac disease, as determined by the Investigator. If patient is deemed to have a high cardiac risk, enrollment may be considered if echocardiogram (ECHO) or multi-gated acquisition (MUGA) during **Screening** demonstrates a cardiac ejection fraction >50%.
11. Patient has a QTc > 470 ms.
12. Patient has a history of other malignancies within the last 1 year, except for non-melanoma skin cancer, carcinoma in situ of the cervix, or PSA-stable, asymptomatic early stage prostate cancer or superficial bladder cancer without active treatment.
13. Patient has clinically significant or recent acute gastrointestinal disease presenting as diarrhea and/or colenteritis as the main symptom (i.e. acute enteritis, malabsorption, or Common Terminology Criteria for Adverse Events (CTCAE, version 5.0) Grade 2 or higher diarrhea due to other drug-related reasons within 15 days.
14. Patient is unable to take drugs orally due to disorders that may affect gastrointestinal function or has malabsorption syndrome.
15. Patient has an active liver disease or biliary tract disease (except for Gilbert's disease, asymptomatic biliary stones, liver metastasis, or stabilized chronic liver disease).
16. Patient has a medical condition that in the opinion of the investigator or medical monitor would put her/him at an unreasonable risk during the trial.
17. Patient has known hypersensitivity to poziotinib or history of allergic reactions attributed to a compound of similar chemical composition to poziotinib.
18. Patient has an active or uncontrolled infection, active bleeding disorder, any underlying medical condition, or other serious illness that would impair the ability of the patient to receive protocol treatment.
19. Patient has had recent major surgery or invasive procedure within 15 days prior to starting study treatment.
20. Patient is pregnant or breast-feeding.

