11. Patient with childbearing potential is willing to practice 2 forms of contraception, one of which must be a barrier method, from study entry until at least 30 days after the last dose of poziotinib.
12. Females of childbearing potential must have a negative serum pregnancy test within 7 days prior to study treatment. Females who are postmenopausal do not require this test (Postmenopausal is defined as any of: age ≥60 years, age <60 years and amenorrheic for 12 or more months in the absence of chemotherapy, tamoxifen, toremifene, or ovarian suppression and follicle-stimulating hormone (FSH) and estradiol in the postmenopausal range, or prior bilateral oophorectomy, or if taking tamoxifen or toremifene, or age <60 years with FSH and plasma estradiol in postmenopausal ranges).

Exclusion Criteria:

1. Patient has primary tumors in central nervous system (CNS), meningeal carcinomatosis, leptomeningeal carcinomatosis, spinal cord compression, or unstable brain metastasis except if qualified under inclusion criteria for Cohort 4.
2. Patients with the T790M mutation in EGFR.
3. Patients with breast or gastric cancers without eligible HER2 mutations (see [Table A](#)).
4. Patient has received anticancer chemotherapy, biologics, immunotherapy, targeted therapy (including HER2 targeted therapy), curative-intent radiotherapy, or other investigational treatment within 15 days of study entry. Palliative local radiation therapy for bone metastasis may be allowed. Standard and approved hormonal therapies for hormonal receptor positive tumors are allowed. For Cohort 4, patients who have prior single agent VEGF inhibitor therapy (eg bevacizumab) are excluded.
5. Patient has used or will continue to use strong inhibitors/inducers of CYP3A4 and CYP2D6 within 2 weeks prior to or during the study.
6. Patient has not recovered (i.e, > Grade 1) from drug-induced pancreatitis or has a history of drug-induced pancreatitis.
7. Patient has interstitial lung disease (ILD) or history of ILD or pneumonitis or is less than 30 days from last dose of CPI.
8. Patient has \geq Grade 2 skin disorders (rash), mucositis, or stomatitis within previous 15 days.
9. Patient has a history of congestive heart failure (CHF) Class III/IV according to the New York Heart Association (NYHA) Functional Classification or serious cardiac arrhythmias requiring treatment.

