5.4.5 Clinical Laboratory Tests

A local laboratory will be used to process all clinical specimens. The following clinical laboratory parameters will be evaluated in this study:

- **Complete Blood Count (CBC):** A CBC, including white blood cells (WBC), with 5-part differential, hemoglobin, and platelets will be performed at Screening, Day 1 and Day 8 of Cycle 1 and Cycle 2, Day 1 of each cycle, and at the End-of-Treatment Visit. The results of the laboratory assessments should be evaluated and medically accepted by the responsible physician before the start of each cycle.
- **Chemistry Panel:** A comprehensive chemistry and electrolytes, including blood urea nitrogen (BUN), AST/SGOT, ALT/SGPT, alkaline phosphatase (ALP), total bilirubin, albumin, calcium, lactate dehydrogenase, sodium, potassium, chloride, phosphate, magnesium, creatinine, uric acid, and glucose, will be performed at Screening Visit, Day 1 of each cycle, and at the End-of-Treatment Visit.
- **Special note for the Day 1 sampling of each cycle:** If possible, blood samples should be drawn on **Day 1** of each cycle (prior to treatment); however, for logistical reasons, it is also acceptable to draw samples for assessment up to 7 days prior to the start of a cycle. The results of the laboratory assessments should be evaluated and medically accepted by the responsible physician before the start of each cycle.
- **Pregnancy Test:** A blood β -hCG test will be performed for all women of childbearing potential at **Screening**. A urine pregnancy test is required on Day 1 of each Cycle starting from **Cycle 2** and at **Cycle 1, Day 1**, if Screening pregnancy test was more than 7 days prior to **Day 1**. Urine pregnancy test also required at **End-of-Treatment Visit**.

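### Inclusion criterion 12 accepts taking tamoxifen or toremifene as proof of menopause, so a premenopausal woman on either drug is exempt from the serum pregnancy test before treatment

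*Combined protocol and SAP*

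**What the plan says.** Section 4.1, criterion 12, asks females of childbearing potential for a negative serum pregnancy test within 7 days before study treatment. It then states: "Females who are postmenopausal do not require this test". A parenthesis defines postmenopausal as any one of a list of conditions. One is being under 60 and "amenorrheic for 12 or more months in the absence of chemotherapy, tamoxifen, toremifene, or ovarian suppression", together with FSH and estradiol in the postmenopausal range. After bilateral oophorectomy, the list closes with "or if taking tamoxifen or toremifene, or age < 60 years with FSH and plasma estradiol in postmenopausal ranges". Synopsis criterion 12 has the same text: "or if taking tamoxifen or toremifene, or age <60 years with FSH and plasma estradiol in postmenopausal ranges".

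Women on these drugs can enter the study. For HER2-negative, ER/PR-positive breast cancer, criterion 4 says: "Patients are permitted to continue single agent endocrine therapy concurrently with the study". Exclusion 4 adds: "Standard and approved hormonal therapies for hormonal receptor positive tumors are allowed". The minimum age is 18, and no criterion excludes premenopausal women.

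Exclusion 20 reads "Patient is pregnant or breast-feeding". Section 7.8 says the potential for harm to an unborn child is unknown, does not recommend poziotinib in pregnancy, and requires pregnancies to be reported within 24 hours.

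**The concern.** The drug clause has an 'or' on each side and no age, amenorrhea or hormone condition of its own. In a list where any one item is enough, taking tamoxifen or toremifene then establishes menopause outright. Yet the amenorrhea item sets aside amenorrhea that occurs on those same drugs, so the sentence treats them both as obscuring menopausal status and as proving it.

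This is an operative eligibility rule. A site that follows it as printed omits the serum test for a woman who may be able to conceive, and commits no deviation in doing so. What is at stake is exposing a pregnancy to a drug whose fetal risk the protocol calls unknown.

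**Working it through.** The plan gives no figure to reproduce. The check is to write the definition as a logical expression and evaluate it.

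**Items in criterion 12 (Section 4.1; same in the Synopsis)**

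- A: age 60 or over
- B: under 60, amenorrhea for at least 12 months off the listed treatments, and FSH and estradiol in range
- C: bilateral oophorectomy
- D: taking tamoxifen or toremifene
- E: under 60, with FSH and estradiol in range

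As printed: postmenopausal = A or B or C or D or E.

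**Test case.** A menstruating woman of 40 on tamoxifen, with no oophorectomy and hormones not in the postmenopausal range: A false, B false, C false, D true, E false. The result is true, so she is exempt. If D and E are joined by 'and', D-and-E is false, the whole expression is false, and the test is required.

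**Redundancy.** B already requires age under 60 and both hormones in range, which is all that E asks. Whenever B is true, E is true, so as printed B never changes the result.

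**All profiles, women under 60 without oophorectomy.** Let M = the amenorrhea condition met off the listed treatments, H = FSH and estradiol in range, T = on tamoxifen or toremifene. M and T cannot both hold, which leaves 3 (M, T) pairs × 2 values of H = 6 profiles.

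- As printed: exempt = (M and H) or T or H, which reduces to T or H.
- With 'and': exempt = (M and H) or (T and H).

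| M | T | H | Exempt as printed | Exempt with 'and' |
|---|---|---|---|---|
| no | no | no | no | no |
| no | no | yes | yes | no |
| no | yes | no | yes | no |
| no | yes | yes | yes | yes |
| yes | no | no | no | no |
| yes | no | yes | yes | yes |
| | | **Total** | **4 of 6** | **2 of 6** |

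Two profiles lose the exemption: on the drug with hormones not in range (the safety gap), and off the drug with hormones in range but without the required amenorrhea. The one change removes both the contradiction and the redundancy, which suggests that the printed 'or' is a drafting slip. That is an inference from the structure of the sentence; the documents do not say so.

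**The case against.** The strongest reply is that little testing is actually lost. The definition sits in parentheses after the exemption from one test. Section 5.4.5 separately says that a blood "test will be performed for all women of childbearing potential" at Screening. A urine test follows at Cycle 1 Day 1 if the Screening test is more than 7 days old, then on Day 1 of each later cycle and at End of Treatment. None of these provisions cites the criterion 12 definition, and a menstruating woman on tamoxifen is of childbearing potential in the ordinary sense. Criterion 11 (contraception) and exclusion 20 also remain, and under Section 5.2 the sponsor confirms eligibility before enrolment.

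Much of this stands. The text itself waives one test only. But childbearing potential is not defined anywhere else, and criterion 12 is the only guidance on who falls outside it, so a site could reasonably apply its list throughout. Exclusion 20 requires no test of its own, and a sponsor check against the printed criterion would reach the same wrong answer.

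It is also fair that 4 of 6 and 2 of 6 count logical combinations, not patients, and that the explicit route through criterion 4 is one subgroup of one cohort, although exclusion 4 is worded more broadly.

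Finally, the 'and' correction removes E as an item on its own, and the documents do not show that E was unintended. Deleting only the drug clause would close the safety gap and keep E. The exemption would then reduce to H, 3 of 6 profiles, but the amenorrhea item would remain redundant.

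**Conclusion.** The criterion is wrong as written, in both places. Followed literally, it exempts a premenopausal woman on tamoxifen or toremifene from the serum test within 7 days before treatment, and it contradicts its own amenorrhea item. This rests on the printed wording alone.

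The practical size is limited and cannot be quantified: the documents do not allow a count of the women affected, and it may be small or zero. Any wider loss, covering the Screening blood test, the urine tests and the contraception rule, assumes that sites use the criterion 12 list to decide who has childbearing potential. The sponsor should correct it as a matter of eligibility and patient safety. Sample size, endpoints and analysis are not affected.

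**What to change.** In Section 4.1, criterion 12, and in Synopsis criterion 12, change the 'or' immediately before the final age condition (the one that follows the drug clause after bilateral oophorectomy) to 'and'. Keep the 'or' that introduces the drug clause, and leave the earlier amenorrhea item alone. The last item then requires three things together: taking tamoxifen or toremifene, age under 60, and both FSH and plasma estradiol in the postmenopausal range.

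The cost is one word in two places and a few more pregnancy or hormone tests. These include tests for women off the drugs whose hormones are in range but who lack the required amenorrhea.
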